6.3.4 Laboratory Data

Clinical laboratory tests on hematology, serum chemistry, electrolytes, and lipids and urinalysis will be performed according to the schedule presented earlier in this SAP. Investigators will assess whether there are any clinically significant abnormalities and record the abnormality on medical history or AE forms.

Conversion to the International System of Units

All laboratory data will be stored in the database with the units in which they are originally reported.

Laboratory data in summary tables and subject data listings will be presented in the International System of

Units (SI units; Système International d'Unités). Laboratory data not reported in SI units will be converted to SI units before further processing or data analysis.

Abnormal Values

Based upon laboratory normal ranges, laboratory test results will be categorized according to the normal range as low, normal and high. Subjects with laboratory data outside the normal range will be listed with abnormal values flagged.

Table 4. Clinical Laboratory Tests

Hematology

Hematocrit (Hct)	Mean corpuscular volume (MCV)
Hemoglobin (Hgb)	Platelet count
Mean corpuscular hemoglobin (MCH)	Red blood cell (RBC) count
Mean corpuscular hemoglobin concentration (MCHC)	White blood cell (WBC) count with differential

Serum Chemistry, Electrolytes, and Lipids

Albumin (ALB)	Calcium (Ca)
Alanine aminotransferase (ALT)	Magnesium
Aspartate aminotransferase (AST)	Phosphorus
Blood urea nitrogen (BUN)	Potassium (K)
Glucose	Sodium (Na)
Total carbon dioxide	Total bilirubin
Creatinine	Direct bilirubin
Chloride (Cl)	Uric acid
Total protein	Low-density lipoprotein cholesterol (LDL-C), calculated
Total cholesterol (TC)	
High-density lipoprotein cholesterol (HDL-C)	
Triglycerides (TG)	

Urinalysis

Appearance	Nitrite
Bilirubin	pH
Color	Protein
Glucose	Specific gravity
Ketones	Urobilinogen
Microscopic examination of sediment	Leukocyte esterase

Urine Drug Screen

Amphetamines	Opiates
Barbiturates	Benzodiazepines
Cocaine Metabolites	Cannabinoids
Cotinine	

Urine Pregnancy Test

Infectious Disease Testing

Hepatitis B Surface Antigen (HbsAg)	Hepatitis C virus (HCV)
-------------------------------------	-------------------------

6.3.5 Vital Signs

Vital signs include pulse (beats/min), SBP and DBP (mmHg), oral temperature (°C) and respiration rate (breaths/min).

Vital sign changes from baseline will be summarized by treatment.

Baseline values are those measured at last evaluation prior to administration of study drug in each treatment period.

Change from baseline to time point t, denoted Change_t, will be calculated as:

$$\text{Change}_t = \text{Value}_t - \text{Value}_{\text{Baseline}}$$

6.3.6 Electrocardiogram

ECG parameters, including the RR interval (intra-beat interval), PR interval (the period that extends from the beginning of the P wave [the onset of atrial depolarization] until the beginning of the QRS complex [the onset of ventricular depolarization]), QRS duration, and QT interval (the corrected QT interval is the measure of the time between the start of the Q wave and the end of the T wave in the heart’s electrical cycle), will be measured according to the study assessment schedule. Each ECG will be assessed by the Investigator for signs of ischemia, clinically significant hypertrophy, and clinically significant T-wave (repolarization of the ventricles) abnormalities. Baseline ECGs will be defined as the last evaluation performed prior to the administration of study drug in each treatment period.

ECG changes from baseline will be summarized by treatment.

Change from baseline to time point t, denoted Change_t, will be calculated as:

$$\text{Change}_t = \text{Value}_t - \text{Value}_{\text{Baseline}}$$

6.3.7 Physical Examination

A complete PE will include measurement of body weight and height (height will be measured only at screening), general assessment of all body systems including the skin, head, eyes, ears, nose, throat, neck, lungs, heart, abdomen, lymph nodes, and extremities.

Physical examination results will be presented in individual subject data listings.

6.3.8 Pregnancy Test

Only pregnancies considered by the investigator as related to study treatment (e.g., resulting from an interaction between study drug and a contraceptive medication) are considered AEs unto themselves.

6.3.9 Concomitant Medications/Treatments

Concomitant medications administered at the time of randomization and during the study will be recorded on the CRF. The medication name, indication, dose, unit, frequency, route of administration, date(s) of administration and reason for administration will be recorded. This documentation should continue until discharge from the study.

A concomitant medication is any medication the subject enters the trial taking and is expected to continue taking for some portion of the trial, as well as any medication other than the investigational product that the subject takes during the course of the trial. All prescription and over-the-counter (OTC) medications (non-prescription drugs), including vitamins and herbal supplements, that subjects receive during the trial must be documented on the CRF. This documentation will continue until the subjects are discharged.

Concomitant medications will be coded using the World Health Organization Drug Dictionary (WHO-DD).

All prior and concomitant medication will be presented in individual subject data listings.

For medications with incomplete dates, imputation will be used to convert to a complete date. Imputed dates will be used to determine Study Day.

Partial medication start dates will be imputed as follows:

1. Only the year is reported: If the subject started to receive study drug in the year reported, then the date of the first dose of study drug will be used as the starting date of the medication. Otherwise, January 1 will be used as the start of the medication.
2. The month and year is reported: If the subject started to receive study drug during the month and year reported, then the date of first dose of study drug will be used as the starting date of the medication. Otherwise, the first day of the month will be used as the start of the medication.

Partial medication end dates will be imputed for non-ongoing medications as follows:

1. Only the year is reported: If the subject stopped to receive study drug in the year reported, then the date of the last dose of study drug will be used as the end date of the medication. Otherwise, December 31 will be used as the end of the medication.
2. The month and year is reported: If the subject stopped to receive study drug during the month and year reported, then the date of last dose of study drug will be used as the end date of the medication. Otherwise, the last day of the month will be used as the end of the medication.

The above rules are subject to logical sense, for example, imputed start date should be on or prior to imputed end date.

Verbatim terms will be coded and assigned a preferred (PT) term and an ATC (anatomic therapeutic class) term.

7. PHARMACOKINETIC ANALYSES

7.1 General Considerations

The PK Population will be used for PK analyses.

Statistical and PK analyses will be performed by Everest Clinical Research. Statistical analysis will be performed using Statistical Analysis Software SAS for Windows® (SAS Institute Inc., USA). Non-compartmental analysis (NCA) will be performed using Phoenix® WinNonlin® 6.4 (Certara, USA).

7.2 Pharmacokinetic Analyses

From the plasma concentration-time data, the following PK parameters will be estimated for each subject where feasible.

Table 5. Pharmacokinetic Parameters

Pharmacokinetic Parameters	
C_{max}	Maximum observed plasma concentration
T_{max}	Time of maximum observed plasma concentration
λ_z	Terminal elimination phase rate constant
$T_{1/2}$	Apparent terminal elimination half life
CL/F	Apparent oral clearance
V_z/F	Apparent volume of distribution
AUC_{0-t}	Area under the plasma concentration-time curve from time 0 to time t (time of last quantifiable plasma concentration)
$AUC_{0-\infty}$	Area under the plasma concentration-time curve from time 0 to infinity

C_{max} and T_{max} will be obtained directly from experimental observations. If multiple maxima occur at equal concentrations, the first temporal value will be taken.

The apparent terminal elimination half-life, $T_{1/2}$, where determinable, will be calculated as the natural log of 2 divided by the terminal phase rate constant, λ_z . The number of data points included in the regression will be determined by visual inspection, but a minimum of three data points in the terminal phase, excluding C_{max} , is required to estimate λ_z . In order for the selection to take place the adjusted r^2 value reported in Phoenix® WinNonlin® must be ≥ 0.7 .

AUC_{0-t} and $AUC_{0-\infty}$ will be calculated using the linear trapezoidal linear interpolation method, using actual elapsed time values. If the actual collection time is unknown the nominal collection time may be used for the purposes of PK parameter estimation. For the purpose of calculating AUC, all missing values will be treated as missing in the PK analysis and excluded from analysis except when they occur at pre-dose where they will be set to zero. All values that were below the limit of quantitation (BLOQ) prior to T_{max} will be set to zero. BLOQ values that occur after T_{max} will be set to missing. When ≥ 2 consecutive plasma concentrations below the limit of quantitation (BLOQ) are encountered after T_{max} , these and all subsequent values will be excluded from the analysis.

$AUC_{0-\infty}$ will be calculated as outlined below:

$AUC_{0-\infty} = AUC_{last} + (C_{last} / \lambda_z)$, where C_{last} is the last temporal quantifiable plasma concentration corresponding to T_{last} .

The proportion of $AUC_{0-\infty}$ due to extrapolation (AUC_{extr}) will be calculated and expressed as a percentage. $AUC_{0-\infty}$ values will be considered unreliable estimates if the AUC_{extr} is greater than 20% and will be excluded from summary tables but will be listed.

CL/F will be calculated as $\text{Dose}/\text{AUC}_{0-\infty}$.

V_z/F will be calculated as $\text{Dose}/(\lambda_z \times \text{AUC}_{0-\infty})$.

$T_{1/2}$ will be calculated as $0.693/\lambda_z$.

Descriptive statistics for the plasma concentrations of digoxin by Treatment, Timepoint and Sex/Gender will be provided. A listing of plasma concentrations by Subject Number, Treatment Period, Timepoint and Sex/Gender will also be provided.

To assess the effect of bexagliflozin on the PK of digoxin, an analyses of variance (ANOVA) using a linear mixed-effects model will be fitted to the natural logarithmic transformation of PK parameters of digoxin (C_{\max} , AUC_{0-t} and $\text{AUC}_{0-\infty}$). The linear mixed-effects model will include subject as a random effect, and treatment, period, and sequence as fixed effects. The 90% confidence intervals will be constructed for digoxin administered with bexagliflozin to digoxin alone ratio of the least squares (LS) geometric means of PK parameters (C_{\max} , AUC_{0-t} and $\text{AUC}_{0-\infty}$), with 80-125% defined as the lack of interaction boundaries.

Descriptive statistics for the PK parameters C_{\max} , T_{\max} , $\text{AUC}_{0-\infty}$, AUC_{0-t} , AUC_{extr} , CL/F, V_z/F , λ_z , and $T_{1/2}$ will be tabulated by treatment. Means, standard deviations, medians, ranges (min, max) and geometric means and coefficients of variation will be presented for all PK parameters with the exception of T_{\max} . Medians and ranges will be presented for T_{\max} .

A listing of derived PK parameters of digoxin by Subject Number, Treatment Period and Sex/Gender will be provided.

The ratios of geometric least squares means and corresponding 90% CI for the treatment comparison will be determined by exponentiating the mean differences between treatments on the logarithm scale. The intra-subject geometric CV%, $100\% * \sqrt{\exp(\text{residual}) - 1}$, where residual = the residual variance component and where exp is the natural exponential function, will be reported.

The appropriateness of the mixed model will be assessed through residual analyses. Any modifications required due to poor fit will be reported and executed.

Refer to Appendix 2 for the SAS code.

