5.5 Blinding

This is an open-label study.

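### Digoxin terminal-phase points are chosen by eye, and neither document masks or freezes that choice; the likely effect is small and masking is cheap

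*SAP*

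**What the plan says.** SAP 7.2 (Pharmacokinetic Analyses) states the selection rule for the lambda-z regression: "The number of data points included in the regression will be determined by visual inspection". Protocol 9.5.1 has the same rule. Both documents require "a minimum of three data points in the terminal phase", leave Cmax out of the regression, and accept a fit only if adjusted r-squared is at least 0.7.

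Lambda-z then enters several results. AUC0-infinity is AUClast plus Clast/lambda-z. Half-life, CL/F, Vz/F and the extrapolated share of AUC all follow from it. An AUC0-infinity value whose extrapolated share "is greater than 20% and will be excluded from summary tables but will be listed". AUC0-infinity is also one of three parameters, with Cmax and AUC0-t, whose 90% interval for the treatment ratio is read "with 80-125% defined as the lack of interaction boundaries".

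On masking, Protocol 5.5 says only "This is an open-label study". SAP 7.1 gives the non-compartmental analysis and the statistics to the same contract organization. SAP section 4 settles protocol violations and PK Population membership before database lock; it does not mention lambda-z windows.

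**The concern.** The window is a judgment made profile by profile, and more than one window can satisfy the written limits. If the person choosing knows which profile is digoxin alone and which is digoxin with bexagliflozin, an expectation about the interaction can enter the choice without anyone intending it. That could move the AUC0-infinity ratio and the half-life summaries in either direction, and could decide which AUC0-infinity values reach the tables. SAP 7.2 does not say whether values above 20% also leave the mixed model, so the choice may also affect which profiles enter that comparison.

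Nothing in the two documents closes this route. There is no masked selection, second reader, fixed tie-break or freeze of the choices before treatments are compared.

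**Working it through.** **Inputs from the documents.** Half-life about 35 h and sampling said to cover 7 half-lives (Protocol 3.2.3); last sample at 120 h (SAP 6.2); LLOQ 0.05 ng/mL (Protocol 6.6.2.3); 18 subjects in two periods, so 36 planned profiles.

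**1. The plan's own figure.** 120 h / 35 h = 3.43 half-lives, not 7; seven would need 7 × 35 = 245 h. The figure does not reproduce, and the half-life, sampling-length and last-sample statements must be reconciled. It matters here because it sets the size of the tail. For a single exponential, the share beyond the last quantifiable sample T is 2^(−T/35):
- T = 120 h: 9.3%
- T = 96 h: 14.9%
- T = 72 h: 24.0%
- at 7 half-lives: 0.8%

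**2. The acceptance limit.** R² = 1 − (1 − adjusted r²)(n − 2)/(n − 1), slope t = √[(n − 2)R²/(1 − R²)], relative SE = 1/t. At adjusted r² = 0.7:
- n = 3: R² = 0.85, t = 2.38, relative SE 42%
- n = 4: R² = 0.80, t = 2.83, relative SE 35%
- n = 5: R² = 0.775, t = 3.21, relative SE 31%

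These are values at the floor. For a typical log-linear tail at 72, 96 and 120 h, the sum of squares in time is 24² + 0 + 24² = 1152, its root is 33.9, and lambda-z = ln 2/35 = 0.0198 per h. Assumed log-scale error of 0.05 to 0.15 gives a relative SE of 0.05/(33.9 × 0.0198) = 7% to 0.15/(33.9 × 0.0198) = 22%.

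**3. From half-life to AUC0-infinity.** Let f be the extrapolated share and k the factor by which another window changes half-life. AUC0-infinity changes by f(k − 1), and the share exceeds 20% when k > 0.25(1 − f)/f.
- f = 9.3%: k = 1.25 raises AUC0-infinity by 2.3%; crossing 20% needs k = 2.44
- f = 15%: 3.8%; crossing needs k = 1.42
- f = 18%: 4.5%; crossing needs k = 1.14

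**4. Simulation.** None of the following is in the documents: bi-exponential disposition with terminal intercept 0.3 to 0.8 ng/mL, 15% between-subject spread around 35 h, residual CV 5 to 15%, 3,000 profiles per setting. The nominal times, linear trapezoids and the SAP's BLOQ rules were applied. All windows starting at 8 h or later that meet the SAP limits were compared.

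| Median last quantifiable sample | Longest/shortest half-life, median (95th percentile) | AUC0-infinity ratio shift if every choice opposes by treatment | Profiles whose 20% verdict depends on the window |
|---|---|---|---|
| 120 h | 1.07–1.20 (1.18–1.60) | 0.8–2.5% | 0.2–4.1% |
| 96 h | 1.09–1.19 (1.20–1.58) | 1.1–2.8% | 0.2–7.1% |
| 72 h | 1.13–1.20 (1.25–1.62) | 2.0–3.9% | 9.8–17.8% |

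Of 36 profiles, 0.2–4.1% is 0.1 to 1.5 profiles and 9.8–17.8% is 3.5 to 6.4.

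A separate simulation chose only among the last three, four or five samples, with 20% between-subject spread. At 35 h it gave 7–20% for half-life, 0.6–1.8% for the ratio and 1–4% for the verdict. At an assumed 45 h, a half-life the documents do not give, it gave 9–23%, 1.3–3.4% and 6–11%. Its profile amplitudes and LLOQ handling are not recorded, so it carries less weight.

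**5. Against the bounds.** With interval width unchanged, a 3.9% upward shift takes an upper limit past 125% only if that limit was already above 125/1.039 = 120.3%. A downward shift of the same factor takes a lower limit below 80% only if it was under 80 × 1.039 = 83.1%.

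**The case against.** The case against acting is substantial, and most of it stands.

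- Two of the three compared parameters do not use lambda-z. A shift created in the tail would show as AUC0-infinity parting from AUC0-t. SAP 7.2 tabulates the extrapolated share by treatment and lists derived parameters by subject, so the tail can be audited.
- The ratio shift needs every window to be chosen in opposite directions by treatment. That describes systematic manipulation rather than an analyst's leaning.
- A reader might infer that the half-life comparison is at risk. SAP 7.2 confines the mixed model and 90% intervals to Cmax, AUC0-t and AUC0-infinity; half-life, CL/F and Vz/F are only described, and no decision rests on them.
- A reader might take the 42% relative standard error as the usual precision of lambda-z. It holds only for a three-point fit exactly at the acceptance floor.
- A reader might infer that the analyst works with treatment known. Protocol 5.5 does not address what the PK analyst receives. SAP section 4 places detailed quality procedures in separate documents not available here, which may or may not cover this step.
- Lambda-z is not the only judgment in the derivation. Nominal times may replace unknown actual times, parameters are estimated where feasible, and PK Population entry depends on having sufficient measurements.

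What remains is that neither document masks or freezes the choice, and the numerical limits usually leave more than one admissible window.

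**Conclusion.** The point holds in a limited form. The regression window is left to visual inspection in an open-label study, with no masking or freeze in either document, and it feeds one of the three ratios read against 80–125%, the descriptive half-life, CL/F and Vz/F, and the 20% rule. The size is about 0.6 to 3.9% at most for the AUC0-infinity ratio, with every choice opposed by treatment, and about 7 to 20% for half-life. The 20% verdict is exposed mainly when quantifiable samples end at about 72 h. These sizes rest on assumed profile shapes, intercepts and residual error.

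The documents do not support a stronger reading, that the interaction conclusion could readily be reversed or that selection will in fact be made with treatment known. The AUC0-infinity reading could change only if an interval limit already lay close to a bound. This is a low-priority improvement, worth making because it costs little.

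**What to change.** Keep the existing criteria in SAP 7.2 and add that lambda-z points are selected on profiles with treatment, period and sequence masked, that each selection is documented, and that all selections are frozen before treatment codes are merged.

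The masked file should carry a scrambled profile identifier and elapsed time from digoxin dosing, without dates or study days. Digoxin on Day 1 or 19 identifies digoxin alone, and Day 3 or 17 identifies the combination, so study day would undo the masking.

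Because Protocol 9.5.1 has the same selection rule, either align that section or record the addition as a change from the protocol under SAP section 10. An algorithmic default, such as the window with the largest adjusted r-squared, is optional: masking alone removes the treatment-related route, and an algorithm would still need documented overrides when it picks an implausibly short window.

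The cost is preparing the masked input file and documenting the change. No new data, subjects or procedures are needed.

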8. STATISTICAL ANALYSIS

8.1 General Data Handling Rules and Definitions

All data collected on CRFs will be provided in listings, except data collected only for confirmation of study entry criteria and for study administrative purposes. If any randomized subject is found to be without valid documented informed consent, that subject's data will be excluded from the report, except as necessary to document the error.

All statistical analyses will be conducted using SAS version 9.4 or newer.

Except where specified, all continuous variables will be summarized with descriptive statistics (the number of non-missing values, mean, standard deviation, median, minimum and maximum) and all categorical variables will be summarized with frequency counts and percentages, by treatment and treatment group. Unless otherwise specified, the mean and median will be displayed to 1 more decimal place than the original data, and standard deviation will be displayed to two more decimal places than the original data. All frequencies will be rounded to 1 decimal place.

Missing data will be maintained as missing unless specified otherwise. For variables where missing data is imputed, the analysis dataset will contain one variable with the imputed value and the original variable with missing maintained as missing.

8.2 Subject Disposition

An overall disposition table for all subjects will be presented. This tabulation will include the number of subjects randomized, treated, completed, and those who discontinued early from the study. The number and percentage of randomized subjects who are included in the PK and Safety Populations will also be tabulated.

Subject disposition by treatment, and treatment sequence, will also be summarized. These tabulations will include the number of subjects dosed, completed, and those who discontinued early from the study along with the corresponding primary reasons for early termination.

Subjects in the Safety Population who prematurely discontinued from the study will be summarized by primary reason for early termination.

Subject disposition will be listed for all subjects in the Safety Population.

8.3 Demographic and Baseline Characteristics

Demographic and baseline characteristics will be summarized by treatment, and by treatment sequence, for both the Safety and PK Populations and listed.

Descriptive statistics (n, mean, median, standard deviation, minimum, and maximum) will be presented for continuous variables. Frequency distributions (counts and percentages) will be presented for categorical variables.

Medical history and baseline conditions will be summarized by treatment sequence and listed. Physical examination, as well as prior and concomitant medications, will also be listed. Prior and concomitant medications will be listed with the drug names and ATC classification codes based on the data collected in the eCRF. The World Health Organization (WHO) Drug Dictionary, version Sept 2017 or newer, will be used to classify prior and concomitant medications by therapeutic class and drug name.

Abnormalities in the subjects' medical and surgical histories will be coded using version 20.1 (or newer) of MedDRA Medical Dictionary for Regulatory Activities, and summarized and listed.

